8.6 Safety Monitoring

8.6.1 Data Safety Monitoring Board (DSMB)

An independent DSMB was installed to review accruing safety information from this trial in parallel to Phase 2 trial VLA15-201 and VLA15-221, and if necessary, to determine whether study or individual subject stopping rules are met. The DSMB reviews all cases of SAEs on an ad-hoc-basis during the main study phase. In addition, the DSMB adjudicates potential cases of LB and AESIs and determines whether cases were new in onset and whether there is any relationship to application of the study vaccine. During the Main Study Phase while study vaccinations are ongoing, the DSMB reviewed listings of SAEs, deaths, AESIs, medically attended AEs, solicited AEs, unsolicited AEs and AEs leading to withdrawal from further vaccination on an approximately monthly basis in scheduled DSMB meetings. During the Booster Phase the DSMB will review all cases of SAEs and AESIs and will be available for ad hoc meetings if requested. After the IND transfer, SAEs will be reviewed by Pfizer Safety and the DSMB will receive copies of the SAE reports for review. AESIs will be reviewed by the DSMB until study end.

A written DSMB charter including a detailed description of DSMB set-up and processes is prepared.

The DSMB reviews the following data:

- Any case reports of SAEs are provided to the DSMB until study end.
- At scheduled meetings, the DSMB reviews listings and summary tabulations of SAEs, AESIs, deaths, solicited AEs, unsolicited AEs and AEs leading to withdrawal from further vaccination.
- Ad-hoc DSMB reviews are initiated if at any time during study conduct enrollment is interrupted by a principal investigator, the sponsor or the medical monitor at the CRO for any safety reasons, or if a pre-specified study stopping rule applies, as described in section 14.2.

The DSMB reviews available safety data and makes recommendations to the sponsor regarding further conduct of the study, further vaccinations in the study and/or protocol modifications to be installed for safety reasons.

8.6.2 Sponsor

Until the last subject of the Main Study Phase reaches Day 180 and during ongoing vaccinations in the Booster Phase, available safety data is reviewed by the sponsor on a regular basis to identify any potential safety concerns and applicability of study stopping rule as described in section 14.2.

8.6.3 Investigator

To ensure information exchange on safety across sites during recruitment and treatment phases, investigators are provided safety listings once a week until the last subject reached Day 180 in the Main Study Phase and while vaccinations are ongoing in the Booster Phase. These listings present information on all grade 3 and 4 solicited and unsolicited adverse events, SAEs and SUSARs reported in the safety database.

9. STATISTICAL METHODS AND SAMPLE SIZE

9.1 General Aspects

The data will be analyzed by a CRO. An SAP will be provided describing in more detail how the study results will be evaluated.

Data will be summarized by treatment group and, where appropriate, by visit and age group. Descriptive statistics (number of observations, mean, standard deviation, minimum, median, and maximum) will be provided for continuous variables (e.g. age and weight). Frequency counts and percentages will be presented for categorical variables (e.g. gender).

All data exclusions, including premature terminations, will be detailed and tabulated. Data listings will include enrolled subjects.

The analyses of baseline characteristics including demographic variables, medical and vaccination history and concomitant medications will be subject to descriptive analyses.

AEs and medical history will be coded using the MedDRA coding dictionary. Concomitant medications (including vaccinations) will be coded using the WHO Drug Dictionary.

More detailed criteria to identify subjects in each analysis population, other research questions of interest not covered in this protocol, the definition of endpoints and details of their calculation, as well as how to deal with missing, unused and spurious data will be covered in the SAP. Generally, missing values of immunogenicity variables will not be imputed, and the analysis will be limited to observed values. For missing data in AE evaluation (e.g. severity information) a worst case approach will be applied. If a change of the planned analyses is considered necessary after protocol finalization, this will be described and justified in the SAP. If a change is made after the final statistical analysis has been performed, this will be described and justified in the CSR.

9.2 Analysis Populations

Safety Population

The safety population includes all subjects who entered into the study and received at least one vaccination. The safety population will be used for all safety and tolerability analyses up to Visit 8 (i.e., Main Study Phase), including demographic data, local/systemic tolerability, laboratory data, (S)AEs and AESIs. All analysis based on the safety population will be carried out using the actual treatment received.

Per-Protocol (PP) Population

The PP population will exclude an enrolled subject if one of the following criteria is met (further criteria may be defined in the SAP):

- Subjects with less than three vaccinations (Day 1, 57 and 180).
- Subjects who received the wrong study medication.
- Subjects who fulfilled exclusion criteria 2, 8, 9, 14.

These criteria for potential protocol violations are identified at the time of planning the study. However, during the course of the trial unforeseen events may occur or new scientific knowledge may become available, therefore final decisions on all protocol violations will be made on a case by case decision in a data review meeting. The PP population serves as primary analysis population for immunogenicity analysis.

Modified Intent-to-Treat (mITT) Population

The ITT population is defined to include all subjects enrolled who received at least one vaccination. Subjects will be analyzed according to the treatment group they had been allocated to, rather than by the actual treatment they received.

Booster Safety Population

All safety analyses of the Booster Phase will be based on the booster safety population, which is defined as all subjects who received the booster vaccination. The booster safety population will be used for all safety and tolerability analyses including demographic data, vital signs, local/systemic tolerability, laboratory data, (S)AEs and AESIs. All analyses based on the safety booster population will be carried out using the actual treatment received.

Booster Per-Protocol (PP) Population

The Booster PP population will exclude any subject if one of the following criteria is met (further criteria may be defined in the SAP):

- Subjects enrolled into the Booster Phase despite exclusion from the PP Population of the Main Study Phase;
- Subjects who received the wrong booster vaccination;
- Subjects who fulfilled the booster exclusion criterion 5;
- Subjects with a forbidden prior or concomitant therapy will be reviewed on a case by case basis

These criteria for potential protocol violations are identified at the time of planning the study. However, during the course of the trial unforeseen events may occur or new scientific knowledge may become available, therefore final decisions on all protocol violations will be made on a case by case decision in a data review meeting. The Booster PP population serves as primary analysis population for immunogenicity analysis of the Booster Phase.

Booster modified Intent-to-Treat (mITT) Population

The mITT population is defined as all subjects who received the booster vaccination. Subjects will be analyzed according to the treatment group they had been allocated to, rather than by the actual treatment they received.

9.3 Immunogenicity Analysis

Immunogenicity analyses include the analysis of OspA serotype (ST1 to ST6) specific IgG levels by ELISA and by a serum bactericidal assay (SBA).

Main Study Phase:

The primary immunogenicity analysis will compare the Geometric Mean Titers (GMTs) of serotype specific IgG against each OspA ST1 to ST6 as determined by ELISA in the PP population between the treatment groups VLA15 w/ alum 135 µg and VLA15 w/ alum 180 µg and between the VLA15 treatment groups and the placebo group, respectively, on Day 208. GMTs and GMT ratios will be estimated by applying an analysis of variance (ANOVA) including the factor treatment group and study site. This will be done using log10 transformed data and taking the anti-log of the resulting point estimates for the least squares means, least squares means differences and the corresponding 95% CIs. Tukey's HSD test will be applied for pair-wise comparisons. In addition, sensitivity analyses (ANOVAs with factors study site, treatment group, study site*treatment group, age, and *B.b. s.I* serostatus at baseline) will be performed.

As secondary analysis, GMTs and GMT ratios will be analyzed by ELISA as outlined above on Day 1, 29, 57, 85, 180, 208, 365 and 545. Analyses will compare both dose groups against each other and against the placebo group.

Further secondary immunogenicity analyses will compare the following:

- The Geometric Mean of the fold rise as compared to baseline (GMFR) for IgG against each OspA ST 1-6 as determined by ELISA (ANOVA).
- Seroconversion Rates against each OspA serotype separately; against all six OspA serotypes combined and against OspA ST1 and ST2 combined. Seroconversion rates will be compared using Fisher-Freeman-Halton tests, a significant overall test will be amended by pair-wise tests (Fisher's exact test).
 - For ELISA: SCR is defined as rate of subjects that change from seronegative* at Visit 1 (baseline) to seropositive†, if seronegative at baseline, or that achieve a four-fold increase in IgG titer compared to baseline, if seropositive at Visit 1
 - For functional antibody testing (SBA): SCR is defined as rate of subjects that change from seronegative to seropositive CCI or as a > 4-fold rise in IgG antibody titer from Visit 1 for subjects that are seropositive at Visit 1 (baseline).
- GMTs, SCRs and GMFRs for IgG against each OspA serotype (ST1 to ST6), determined by ELISA, at Day 1, 29, 57, 85, 180, 208, 365 and 545, stratified by age group.

All immunogenicity analyses will be performed for the PP population. It will be described in the SAP which analyses will be repeated for the mITT population and which analyses will also be repeated stratified by baseline *B.b. s.l.* serostatus and by age. Study sites with low enrollment numbers per randomization stratum will be combined in these analyses, further details will be provided in the SAP.

Booster Phase:

The primary immunogenicity analysis will provide 95 % Confidence Intervals for Geometric Mean Titers (GMTs) of serotype specific IgG against each OspA ST1 to ST6 as determined by ELISA in the Booster PP population at Visit 10 (Month 19). GMTs and GMT ratios will be estimated by applying an analysis of variance (ANOVA) including the factor treatment group and study site. This will be done using log10 transformed data and taking the anti-log of the resulting point estimates for the least squares means, least squares means differences and the corresponding 95 % CIs. In addition, sensitivity analyses (ANOVAs with factors study site, treatment group, study site*treatment group, age, and *B.b. s.l* serostatus at baseline) will be performed.

As secondary analysis, GMTs and 95%CI will be provided at Month 18 (Visit 9), Month 24 (Visit 11), and Month 30 (Visit 12). Analyses will compare the VLA15 group against the placebo group.

Further secondary immunogenicity analyses will provide the following:

- The Geometric Mean of the fold rise (GMFR) at Visit 10 (Month 19) as compared to Visit 1 (baseline), Visit 6 (Day 208, peak titer after primary immunization series) and Visit 9 (pre-boost) for IgG against each OspA ST 1-6 as determined by ELISA (ANOVA) and SBA, if applicable.
- Seroconversion Rates against each OspA serotype separately at all study visits (ELISA and SBA).
- GMTs for IgG against each OspA serotype (ST1 to ST6), determined by ELISA, at specified time points, by age group.

* An ELISA titer below 40 U/mL (i.e., the quantitation limit of the ELISA) is considered "OspA IgG seronegative". Values will be replaced by 20 U/mL.

† An ELISA ≥40 U/mL is considered "OspA IgG seropositive".

All immunogenicity analyses of the Booster Phase will be performed for the Booster PP Population. It will be described in the SAP whether any analyses will be repeated for the Booster mITT.

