4. INVESTIGATIONAL PLAN

4.1 Study Endpoints

Primary Endpoint:

- + GMTs (Geometric Mean Titers) for IgG against each OspA serotype ST1 to ST6, determined by ELISA at Day 208 (Month 7).

Secondary Endpoints:

Immunogenicity:

Main Study Phase:

- + GMTs for IgG against each OspA serotype (ST1 to ST6), determined by ELISA, at Day 1 (Month 0), 29 (Month 1), 57 (Month 2), 85 (Month 3), 180 (Month 6), 365 (Month 12), and 545 (Month 18).
- + SCRs (Seroconversion Rate, defined as rate of subjects that change from seronegative[†] at Visit 1 (baseline) to seropositive[†], if seronegative at baseline, or that achieve a four-fold increase in IgG titer compared to baseline, if seropositive at Visit 1 for each OspA serotype specific IgG (ST1 to ST6), determined by ELISA, at Day 29 (Month 1), 57 (Month 2), 85 (Month 3), 180 (Month 6), 208 (Month 7), 365 (Month 12), and 545 (Month 18).
- + GMFR (Geometric Mean of the fold rise) as compared to baseline for IgG against each OspA serotype (ST1 to ST6), determined by ELISA, at Day 29 (Month 1), 57 (Month 2), 85 (Month 3), 180 (Month 6), 208 (Month 7), 365 (Month 12), and 545 (Month 18).
- + GMTs, SCRs and GMFRs for IgG against each OspA serotype (ST1 to ST6), determined by ELISA, at Day 1 (Month 0), 29 (Month 1), 57 (Month 2), 85 (Month 3), 180 (Month 6), 208 (Month 7), 365 (Month 12), and 545 (Month 18) stratified by age group.

Booster Phase (applicable for a subset of subjects participating in booster phase):

- + GMTs for IgG against each OspA serotype (ST1 to ST6), determined by ELISA, at Day 1 (Month 0), 29 (Month 1), 57 (Month 2), 85 (Month 3), 180 (Month 6), 365 (Month 12), 545 (Month 18), Month 19, Month 24 and Month 30.
- + SCRs for each OspA serotype specific IgG (ST1 to ST6), determined by ELISA, at Day 29 (Month 1), 57 (Month 2), 85 (Month 3), 180 (Month 6), 208 (Month 7), 365 (Month 12), 545 (Month 18), Month 19, Month 24 and Month 30.
- + GMFR as compared to baseline for IgG against each OspA serotype (ST1 to ST6), determined by ELISA, at Day 29 (Month 1), 57 (Month 2), 85 (Month 3), 180 (Month 6), 208 (Month 7), 365 (Month 12), 545 (Month 18), Month 19, Month 24 and Month 30.
- + GMFR as compared to Day 208 for IgG against each OspA serotype (ST1 to ST6), determined by ELISA at Month 19, Month 24 and Month 30;
- + GMFR as compared to Month 18 (pre-boost) for IgG against each OspA serotype (ST1 to ST6), determined by ELISA at Month 19, Month 24 and Month 30;

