* If applicable, HIV test, Lyme borreliosis screening test, serum pregnancy test, clinical chemistry tests, hematology tests, and coagulation tests performed at the study site within the study VLA15-202 is acceptable for study VLA15-201 if within the specified visit window. As such, if test results are available, respective blood samples do not need to be collected again for the present study. Similar, if applicable, a baseline serology sample collected at the study site within the study VLA15-202 is acceptable for study VLA15-201 if within the specified visit window.

† A woman that is considered of non-childbearing potential must be e.g. surgically sterilized for at least 3 months prior to Visit 1 (e.g. by hysterectomy, bilateral salpingectomy, bilateral oophorectomy, transcervical sterilization), or postmenopausal for at least one year prior to Visit 1.

- Urine pregnancy test: In women of childbearing potential. Pregnancy test result must be obtained prior to vaccination.
- Collect immunogenicity blood sample (before vaccination).
- **Designated unblinded staff member only**: Randomize subject to treatment group as described in section 4.2.9. As this study is performed observer-blind, subjects must not be informed about the treatment group they have been allocated to.
- **Designated unblinded staff member only**: Prepare and administer first vaccination according to assigned treatment group into deltoid of the non-dominant arm.
 - Blinded staff member takes over subject: Observe subject for 30 min after vaccination for immediate treatment of possible AEs.
- Record any AEs and local and systemic tolerability following vaccination, if applicable.
- Distribute Subject Diary, thermometer and measuring device: Instruct subject how and when to complete the diary. Subject is also instructed to immediately inform the site in case they experience any severe solicited AEs (see Section 8.3.2 for severity grading of AE) or other severe symptoms or if subject has any suspicion of having Lyme borreliosis.
- If the subject has any complaints after vaccination, perform a symptom-driven physical examination and record vital signs prior to discharge. Only discharge subject if in the opinion of the investigator no further concerns exist.

Visit 2, Day 29/ Month 1 (+/- 4 days):

This visit is performed as an in-person visit at the study site.

- Document any changes to concomitant medication/treatments including vaccination(s) since the previous study visit.

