7. ASSESSMENT OF IMMUNOGENICITY

7.1 Immunogenicity Measurements

Immunogenicity assessments measuring OspA serotype specific by IgG ELISA are performed on samples collected at Visits 1-12, or at respective unscheduled visits after Visit 7 or 8, if one or more of these visits are performed remotely (e.g., phone/ video calls).

[figure not shown]
All steps of the assays are performed at Valneva Austria GmbH Vienna, Department of Clinical Serology according to Standard Operating Procedures (SOPs). The work is performed in an environment that is certified to Biological Safety Level 2 (BSL2), internally audited, and conform to GCLP requirements. Raw data is stored on a separate, secure server in a defined Information Technology environment complying with regulatory standards. Raw data print outs are stored in respective study binders.

Details on the analysis of immunogenicity assessments described below will be provided in the Statistical Analysis Plan (SAP).

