7.1.1 OspA serotype specific IgG antibodies (ELISA)

For the evaluation of immunogenicity, human sera is analyzed for IgG against each OspA serotype (ST1 to ST6) separately by ELISA. Dilution series of sera are added to microtiter plates coated with full length OspA ST1/ST2/ST3/ST4/ST5 or ST6. Presence of binding IgGs are detected with an anti-human IgG enzyme conjugate followed by addition of the substrate. The optical density of the colored end product is proportional to the amount of protein specific IgG present in the serum that can be quantified on the basis of the Reference Substance curve by four-parameter logistic fit and parallel line analysis. As this Phase 2 study is intended to support dose selection for Phase 3, the assay was validated and filed to the IND prior to testing.

CCI

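### The GMT models leave out the Day 1 same-serotype OspA IgG titre; this forgoes a probably small, nearly free gain in precision and is not an error

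*Protocol*

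**What the plan says.** Protocol section 9.3 (Main Study Phase) analyses log10 titres at Day 208 as follows: "GMTs and GMT ratios will be estimated by applying an analysis of variance (ANOVA) including the factor treatment group and study site". Pairwise comparisons use Tukey's HSD. The supporting models are "sensitivity analyses (ANOVAs with factors study site, treatment group, study site*treatment group, age", plus baseline B.b. s.l. serostatus. The same approach carries to the other visits: "GMTs and GMT ratios will be analyzed by ELISA as outlined above on Day 1, 29, 57, 85, 180, 208, 365 and 545".

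The Day 1 titre is available. Section 4.2.3 has the Visit 1 immunogenicity sample drawn before the first injection. Section 7.1 states that "IgG ELISA are performed on samples collected at Visits 1-12", and section 7.1.1 that "human sera is analyzed for IgG against each OspA serotype (ST1 to ST6) separately by ELISA".

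In section 9.3 the Day 1 titre has three uses: as an outcome in its own right, in the definition of seroconversion, and as the denominator of the fold rise (GMFR). It is not a covariate in any stated model.

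**The concern.** When the outcome is also measured before treatment, using that measurement as a covariate keeps a randomised comparison unbiased. It removes chance imbalance and any residual variance that baseline explains. The 135 versus 180 µg contrast at Day 208 is the one on which section 9.6 bases the sample size, so the width of its interval matters.

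The terms already planned do not do the same job:

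- B.b. s.l. serostatus is a positive or negative result from a commercial screening test. It is not a quantitative titre for the serotype analysed, and it enters only the sensitivity models.
- The GMFR analysis uses the Day 1 titre with its slope fixed at 1 on the log scale. That gives a wider interval than the unadjusted analysis whenever the true slope is below 0.5.

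The synopsis aims for about 10% or more of subjects seropositive for B.b. s.l. at baseline, so some spread in pre-existing antibody is possible.

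**Working it through.** **Inputs from protocol section 9.6.** GMT 61.3 versus 100.4, SD 0.51 on the log10 scale, 90 evaluable per dose arm, two-sided 5%.

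**1. The plan's own figure.**
- Difference = log10(100.4/61.3) = 0.2143.
- Standard error = 0.51 × √(2/90) = 0.0760.
- Noncentrality = 0.2143/0.0760 = 2.82.
- Two-sample t-test with 178 df: power 80.0%. The stated 80% is reproduced, and it does not rely on baseline adjustment.

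**2. Power under the planned pairwise test.** Tukey's HSD over three groups, assuming 90, 90 and 45 subjects (50 placebo less 10%), has 222 df and a critical value of about 2.36. Power at the same inputs is about 68%.

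**3. Effect of the covariate.** The residual SD becomes 0.51 × √(1 − ρ²), where ρ is the within-group correlation of log10 Day 1 and Day 208 titre. The protocol gives no ρ, so a range is assumed. The last column is 10^(1.96 × SE), the factor on either side of the GMT ratio for an unadjusted 95% interval.

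| Assumed ρ | Interval width (log scale) | Power, t-test | Power, Tukey | 95% CI multiplier |
|---|---|---|---|---|
| 0 | 1.000 | 80.0% | 67.7% | 1.409 |
| 0.1 | 0.995 | 80.4% | 68.2% | 1.407 |
| 0.2 | 0.980 | 81.6% | 69.7% | 1.400 |
| 0.3 | 0.954 | 83.6% | 72.4% | 1.387 |
| 0.35 | 0.937 | 84.9% | 74.1% | 1.379 |
| 0.5 | 0.866 | 89.9% | 81.4% | 1.346 |

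**4. Which ρ is plausible.** Section 9.3 replaces titres below 40 U/mL by 20, so undetectable baselines are all equal. Two illustrations, both resting on assumptions:
- If 10% of subjects are positive at Day 1 and end 0.3 to 0.6 log10 higher, ρ = √(0.1 × 0.9) × 0.3/0.51 = 0.18, up to √(0.1 × 0.9) × 0.6/0.51 = 0.35.
- If 10% are detectable, with exponential log10 titres (mean 0.3) above 40 U/mL and total SD held at 0.51, simulated ρ is 0.12 at slope 0.3, 0.20 at slope 0.5 and 0.40 at slope 1.

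A range of about 0.1 to 0.35 is therefore reasonable, and 0.5 is optimistic.

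**5. Three-arm check.** I simulated 90/90/45 subjects with that baseline distribution and placebo Day 208 titres following Day 1. A common-slope ANCOVA lowered the standard error of the dose contrast by up to about 2% at vaccine-arm slopes of 0.3 to 0.5, and by about 8% at slope 1. With no relation in the vaccine arms, the standard error rose by less than 1%. At a vaccine-arm slope of 0.3, placebo pulled the fitted common slope up to about 0.44.

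**The case against.** The best case against raising this is that nothing in the plan is wrong and that the benefit is unproven.

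- **Validity.** Randomisation makes the treatment-plus-site ANOVA unbiased. This stands in full. A reader might infer bias or an invalid primary analysis, and the protocol supports neither.
- **Size.** No correlation is given, and the floor at 20 U/mL may leave Day 1 titres nearly constant. Section 1.2 says OspA is downregulated during tick feeding, and section 4.2.2 expects no boosting from natural infection, so past infection may be a poor guide to OspA IgG. All sites are in the US, where section 1.1 attributes almost all cases to ST1, so any gain for ST2 to ST6 is less certain still. This also stands. It is why the 90% power seen at ρ = 0.5 should not be the headline.
- **Existing handling of baseline.** Randomisation is stratified by serostatus, age group and site. Serostatus enters the sensitivity models, and GMFR and seroconversion use the Day 1 titre. This helps but does not replace the covariate. Section 7.1 defers further analysis detail to the SAP, which is not at hand, but section 9.3 itself names the model terms.
- **Common slope.** One slope shared with placebo is imperfect, because placebo titres should follow baseline more closely than vaccine-arm titres. This stands, and the fix has to deal with it.
- **Timing.** Section 9.7 records the Day 208 analysis as done, and section 9.5 reports that 180 µg was selected. A reader might infer that the omission affected that choice. The documents do not support this. Section 9.5 gives the reasons as the highest dose, good safety and good immunogenicity, and section 1.4.3.2 reports Day 208 ST1 GMTs of 276.4 and 274.7, a ratio of 0.99.

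**Conclusion.** The point holds as a small missed gain in precision. The section 9.3 models are sound, and the 80% power figure reproduces without any baseline adjustment. An already measured baseline of the outcome is left unused in the GMT models. For ρ between 0.1 and 0.35, intervals would be about 0.5 to 6% narrower. Unadjusted power would be about 80 to 85% instead of 80%, and Tukey power about 68 to 74% instead of about 68%.

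These figures rest on an assumed correlation, on the protocol's Phase 1 SD, and on calculations that leave out the site factor; the ρ that matters is the one remaining after site. The gap between 80% and 68% comes from the Tukey adjustment and is a separate matter from the covariate. This is a cheap improvement of low priority.

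**What to change.** In section 9.3 or the SAP:

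1. For GMT models at time points not yet analysed, add the log10 Day 1 titre of the same serotype as a covariate. An indicator for a Day 1 titre below 40 U/mL is optional.
2. Estimate the 135 versus 180 µg contrast with a slope that placebo does not determine. Either include a baseline-by-vaccine/placebo term or fit the two dose arms alone.
3. For Day 208, keep the ANOVA already run as the primary result. Report the ANCOVA beside it only as a labelled post hoc sensitivity analysis. Section 1.4.3.2 already reports Day 85 GMTs, so the same treatment suits that visit.
4. State how a missing Day 1 titre is handled. Few are expected, since the sample is drawn before the first injection.

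The cost is a few words in the model statement, one or two model degrees of freedom (one more if the indicator and the interaction are both used), and up to about 1% of precision if baseline proves unrelated to outcome. No new data are needed.
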